
Sub-study B: Behavioral task, ECoG recording, and data processing.

Experimental procedure. The study consists of two sessions on different days. The generic task design will be as follows: In the first session, each trial begins with a fixation cross and serial presentation of two sample items, followed by a brief delay (Delay1pre-cue), followed by a cue (Cue1) indicating which item will be tested first, followed by an additional delay (Delay1post-cue), followed by a memory probe

requiring a “same/different” response (Probe1) followed by Delay2pre-cue, Cue2, Delay2post-cue, and Probe2. The timing will be as follows: Fixation (.5 sec); Sample1 (.5 sec); ISI (.1 sec), Sample2 (.5 sec); Delay1pre-cue (.5 sec), Cue1 (.5 sec), Delay1post-cue (2.5 sec), Probe1 (2 sec); Delay2pre-cue (.5 sec); Cue2 (.5 sec); Delay2post-cue (2.5 sec); and Probe2 (2 sec). Thus, total time per trial = 12.6 sec. (Note that the duration of the Delaypost-cue epochs is necessitated by the fact that behavioral [31, 45] and EEG data [31] indicate that it takes between 1-2 sec for an item to transition from AMI to UMI.). This timing will allow for the collection of 96-106 trials within a span of 30 min, a block that can be interrupted and restarted as needed to suit the comfort of the patient. (Previous experience from ECoG studies performed by colleagues of the PI who are based at the University of California indicates that the “20-min mark” is a conservative estimate of the duration of a testing session that a patient can be expected to tolerate; many patients can tolerate either longer sessions, or multiple sessions separated in time.) Critically, the ECoG study that discovered and characterized the phase-encoded selection mechanism that we will investigate in the present study [70] made this discovery in data from four patients, with a design that yielded 40-50 trials/condition/patient; thus our design, intended to collect a minimum of 96 trials, will be adequately powered to detect effects of interest at the single-subject level. (SNR of ECoG signals will be considered further along in this section.)

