For each stimulus domain, each sample stimulus will only appear once in the experiment. The stimuli were determined from previous studies using similar tasks to yield 75-90% correct performance in an independent set of healthy young adults. On each trial, two stimuli from the three categories will be presented, and cuing will be randomly determined, such that on each trial one item serves as the AMI, one as the UML, and one as the “irrelevant” category (i.e., the category that was not presented on that trial).

- Face stimuli will be photographs of highly discriminable faces with different genders and races. The probe stimuli will either be a same face, or a difference face with the same gender and race.

- Scene stimuli will be photographs of highly discriminable natural scenes. The probe stimuli will either be a same scene, or a difference scene from the same scene category.
- Word stimuli will be words that have homonyms. The probe stimuli will either be the homonym of the sample word, or a different word.

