Stage 1. Because we do not know, *a priori*, the characteristics of the neural code underlying the representation of stimulus information in working memory, Stage 1 of the analyses will necessarily have an exploratory quality. At a general level, however, we have principled reasons for first applying MVPA to the ECoG data, and, second, as a back-up plan, applying ROC-based analyses of electrode selectivity. The rationale for starting with MVPA is twofold: first, the novel insights derived from [31-33, 60] were made possible by the application of MVPA; second, MVPA is quite simply more compatible than are univariate methods with the near-universally accepted idea that the brain represents information via distributed patterns of neural activity [e.g., 25, 29, 43]. The first step with MVPA will be to train classifiers to discriminate each stimulus with high-gamma values measured at each electrode in the array during the sample presentation epochs, then to feed data from the delay periods to the sample-trained classifiers. Although this train-on-sample-test-on-delay approach has been successful for decoding stimulus information from fMRI and EEG datasets [e.g., 17, 31, 33, 34, 36, 37, 58, 60], it does assume that the neural representation of information being held in working memory will be the same as it is when that information is being perceived and encoded. Therefore, we will also be prepared to employ a hold-one-trial-out cross validation approach, in which MVPA classifiers will be iteratively trained and tested on data from the Delaypost-cue epochs. The duration of an analysis “epoch” and, indeed, the very data that will be used to train MVPA classifiers, cannot be known until we begin working with these data. For example, with fMRI, MVPA cross validation can be performed on a TR-by-TR basis, the highest temporal resolution possible with fMRI [e.g., 17, 33, 34, 36, 37, 58]. With EEG, however, MVPA performance varies with the width of the sliding window within which spectral power is computed [31, 60], presenting a tradeoff of temporal resolution for classifier performance. Furthermore, because ECoG presents such a rich array of measures, we can’t know *a priori* whether MVPA might be most effective when applied to, e.g., broadband power [39], PAC [66], an event-related potential (ERP), or some other measure.

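### Sub-study B, Stage 1: no trial hold-out is stated for the lead classifier (train on sample, test on delay), so noise that persists within a trial can pass for evidence that the unattended item is represented

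*Combined protocol and SAP*

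**What the plan says.** The decoding plan is in Statistical Considerations, Sub-study B, Stage 1. The lead step fits classifiers to high-gamma values recorded "during the sample presentation epochs, then to feed data from the delay periods to the sample-trained classifiers". Nothing is said about which trials are used for fitting and which for testing.

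The next sentences note that the neural code may differ between perception and memory, and for that reason add an alternative: "Therefore, we will also be prepared to employ a hold-one-trial-out cross validation approach". That hold-out belongs to a classifier trained and tested on the post-cue delay. The plan also leaves the inputs open: "the very data that will be used to train MVPA classifiers, cannot be known until we begin working with these data".

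The task is set out under Sub-study B in Research Design and Methods. On each trial "two stimuli from the three categories will be presented, and cuing will be randomly determined", so that "on each trial one item serves as the AMI, one as the UML, and one as the “irrelevant” category" (UML is the document's variant spelling of UMI). Because "each sample stimulus will only appear once in the experiment", the label that can be decoded is the category, not the individual picture or word. No localizer or other separate training run is described for this sub-study.

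At the end of Stage 1, if decoding succeeds, the top tenth of electrodes by classifier importance goes to Stage 2. If the classifiers are not stable, an ROC analysis selects the electrodes instead.

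**The concern.** Using different epochs for training and testing does not make them independent when both come from the same trial. The two samples and the post-cue delays share one 12.6-second trial, the same electrodes and the same slow state. Whatever is peculiar to trial *i* on the day enters training under the two categories shown on that trial and never under the third. If it is still present in the delay, the classifier partly recognises the trial and returns its two labels.

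Specific Aims asks whether unattended items are represented by elevated activity or not. The artefact pushes towards one answer, UMI evidence above the irrelevant category. It lifts AMI and UMI equally, so the AMI-versus-UMI contrast would not reveal it. Stage 1 gives no chance level, permutation null or other reference that might absorb it. A classifier that only appears to succeed would also tilt the choice between classifier-selected and ROC-selected electrodes.

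**Working it through.** The plan gives no decoding accuracy, test or error rate for Stage 1, so there is no figure to reproduce.

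**Inputs from the documents**
- Three categories, two shown per trial, cue random (Sub-study B).
- Trial length: 0.5+0.5+0.1+0.5+0.5+0.5+2.5+2+0.5+0.5+2.5+2 = 12.6 s, as stated.
- Trials per patient: "our design, intended to collect a minimum of 96 trials" in the design section, but a minimum of 40 in Statistical Considerations. Both are used.
- Up to 128 research channels (Data collection and processing).

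**Assumptions not in the documents**
- ρ, the share of noise variance common to all epochs of a trial, from 0 to 0.5.
- 64 to 128 usable channels; a ridge classifier; trial noise independent across channels unless stated otherwise.
- A trial-level t-test of UMI minus irrelevant evidence.
- No category information at all in the delay, so every rejection is false.

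**Hand calculation.** Take a class-mean classifier, *T* trials, *P* channels, unit noise variance, and a category signal of *s* SD on *k* channels during the sample only. Each category has n = 2T/3 training epochs.
- The tested trial supplies 1/n of the mean of each category it showed and nothing to the third. Expected gap, UMI minus irrelevant: ρP/n.
- Variance of the gap, approximately: 2P/n + 2ks².
- Expected test statistic: z = √T · (ρP/n) / √(2P/n + 2ks²).

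With T = 96, P = 100, k = 10: n = 64 and 2P/n = 3.125.
- ρ = 0.2, s = 0: gap 0.3125, z = 9.80 × 0.3125/√3.125 = 1.73, two-sided rejection 41%.
- ρ = 0.2, s = 0.7: variance 3.125 + 9.8 = 12.925, z = 0.85, rejection 14%.
- ρ = 0.05, s = 0.7: z = 0.21, rejection 5.5%.

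**Simulation A** (ridge, 96 trials, 100 channels, 500 runs, two-sided 5%). False-positive rate without hold-out:

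| Sample signal | ρ = 0.05 | ρ = 0.2 | ρ = 0.5 |
|---|---|---|---|
| none | 8% | 36% | 99.6% |
| 0.4 SD | 5% | 21% | 75% |
| 0.7 SD | 5% | 10% | 43% |

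With trials held out, every cell is 4–7% and accuracy is 50%. The hand results (41%, 14%, 5.5%) lie close to the matching cells (36%, 10%, 5%).

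**Simulation B** (ridge penalty 10 or 200, 64 or 128 channels, 40 or 96 trials, random category signal on about a fifth of channels, 200 runs, one-sided 5%):

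| ρ | UMI above irrelevant | Test rejects | Rejects, 40 trials | Rejects, 96 trials |
|---|---|---|---|---|
| 0 | 49–51% | 3.5–12.5% | 5–11% | 3.5–12.5% |
| 0.1 | 51–56% | 7.5–22% | 9.5–22% | 7.5–14% |
| 0.3 | 53–62% | 18–62% | 24.5–62% | 18–33.5% |
| 0.5 | 55–69% | 31–91% | 38.5–90.5% | 31–65.5% |

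With whole trials held out (8-fold by trial), UMI beats irrelevant in 48.9–50.8% of trials and the test rejects in 2–7.5% of runs at every ρ. AMI against UMI stays at 49–52% throughout.

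With 200 runs the standard error near 5% is √(0.05×0.95/200) = 1.5 points. Two cells at ρ = 0 still read 11% and 12.5%. Shared noise cannot explain these, so the excess at ρ = 0.1 should be read with caution. The rise at 0.3 and 0.5 is well beyond it.

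**Simulation C** (setup of A, 200 runs) tests the assumptions that drive the size:
- Stronger sample signal: at ρ = 0.2, 6.5% at 1.5 SD and 5% at 2 SD; at ρ = 0.5 and 1.5 SD, 15.5%.
- Trial noise in three spatial components: 3.5–10% in all settings, including ρ = 0.5.
- Trial noise in ten components: 5.5% and 11% at 0.7 SD (ρ = 0.2 and 0.5); up to 33.5% with no sample signal.

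**The case against.** **The plan does not say that trials are reused.** A reader might infer that it prescribes training and testing on the same trials. It does not. It is silent on the split and leaves the training data open. It also refers, for data collection and analysis procedures, to a grant application that is not available here. This stands, and the point is therefore that no hold-out is stated. The silence still matters, because a hold-out is spelled out for the alternative and the reason given there is a possible change of code, not leakage.

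**Stage 2 goes ahead either way.** A reader might infer that false decoding success opens Stage 2. The ROC back-up leads there too, so the result decides only how electrodes are chosen. In a further check with simulation A's setup, 9.8 to 10 of the top 10 electrodes per category were the same with and without hold-out. The electrode list within the classifier route therefore hardly moves.

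**The formal test is elsewhere.** Stage 1 is described as partly exploratory, and the stated hypothesis concerns high-gamma power and interregional phase-amplitude coupling in Stage 2. A reader might infer that the study's main test is invalid; the documents do not support that. What remains is that Stage 1 decoding bears directly on the question in Specific Aims and would be read that way. The t-test used above is itself an assumption.

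**The largest rates are extreme cases.** Near-certain false decoding needs a correlation of 0.5, noise independent across electrodes and no category signal while the pictures and words are being viewed. A slow brain state is more likely to be spatially correlated, which shrinks the effect. Inflation from subtracting each trial's fixation baseline cannot be claimed either, since no such step is specified for the classifiers.

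**Conclusion.** The point holds as a gap with a known direction. As written, the lead step allows epochs of one trial in both training and test. Noise that persists within the trial then favours both presented categories over the irrelevant one.

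The size cannot be fixed from the documents, because it depends on a within-trial correlation and a spatial noise structure that they do not give. Over correlations of 0.05 to 0.5, the false-positive rate of a nominal 5% UMI-versus-irrelevant test runs from about 5% (low correlation, strong sample signal, or noise in few spatial components) to well above 30% (correlation 0.5, spatially independent noise, weak sample signal). It is generally larger at 40 trials than at 96. With trials held out it is about 5% in all the settings simulated.

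What is at risk is the Stage 1 decoding evidence on the unattended item, and the choice between classifier-selected and ROC-selected electrodes. The AMI-versus-UMI contrast, the occurrence of Stage 2 and its separate power and coupling tests are not put in doubt by this point. It should be corrected before the data are analysed.

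**What to change.** In Statistical Considerations, Sub-study B, Stage 1, add to the lead step:
- When a classifier trained on sample epochs is tested on a delay epoch, all epochs of the tested trial are excluded from training (leave-one-trial-out, or k-fold by trial).
- Scaling and feature selection are done within the training trials only.
- Decoding counts as successful, for the choice of electrodes at the end of Stage 1, only on these held-out results.

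It would help to state the chance level and a trial-level permutation reference in the same place.

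The cost is a short addition to the text and more computing time. Leave-one-trial-out removes at most two training epochs per fold: 2 of 2×96 = 192 (1.0%), or 2 of 2×40 = 80 (2.5%). No new data or patients are needed.

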#### Statistical Considerations:

Sub-study A: The analyses will proceed in two stages. The first will be to determine the spatial selectivity of each ECoG electrode by calculating its response, in high-frequency (70-250 Hz) broadband power to each of the four locations stimulated during the Receptive Field Mapping task. Also of interest will be fluctuations in alpha-band power (8-13 Hz), and in phase-amplitude coupling (PAC) between alpha-band oscillations in the ECoG signal and high-frequency broadband power.

Data analysis from the Attention Task will focus on electrodes identified in the Receptive Field Mapping task to be preferentially responsive to one, or a subset, of the four critical locations. For each of these electrodes, values of alpha-band power and PAC will be analyzed as a function of attentional condition: attended (i.e., cued with 75% likelihood); ignored (i.e., cued with 25% likelihood); or irrelevant. Although a recent study has looked at alpha-band power as a function of attended vs. ignored [14], the proposed study will differ from this in two important ways. First, our critical comparison is between ignored vs. irrelevant; second, all conditions in our task will be within the same informational domain and sensory modality (i.e., visuospatial perception), whereas that of [14] spanned both (i.e., it used switches between an auditory and a motor task). Because this previous study collected 190 trials per subject [14], we believe that our design, which will collect a total of 384 trials, will be sufficiently powered to carry out the analyses of interest.

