If we are successful, with MVPA, at decoding the identity of each of the three stimuli in the stimulus set, we will use the top 10% of electrodes contributing to the discrimination of each stimulus for Stage 2 of the analysis. (I.e., we will use the electrodes with the highest loadings in the importance map of the trained classifier corresponding to each stimulus.) Should the MVPA analyses not yield stable results, however, our back-up plan for Stage 1 will be to quantify each electrode’s selectivity for each item in the stimulus set with receiver operating characteristic (ROC)-based analyses. Such analyses have long been used to quantify the selectivity of single neurons recorded with extracellular electrodes, and a very similar approach has been used successfully in studies carried out by investigators from the ECoG consortium from which patients will be recruited for this project. For example, Parvizi and colleagues [51] indexed the selectivity of electrodes located in mid-fusiform gyrus, for faces vs. non-face stimuli, with a “signal-to-noise ratio” analysis of broadband oscillatory signals in the 40-160 Hz range. Voytek et al. [70] found that condition-specific fluctuations in the magnitude of PAC indexed selectivity of PFC electrodes for specific S-R mapping rules. Therefore, we also expect that oscillatory power in the 40-160 Hz range will be effective for deriving robust ROC estimates.

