Stage 2. Having identified stimulus-selective electrodes in Stage 1 of our analyses, Stage 2 will effect the test of the phase-encoded selection hypothesis. Specifically, we will test the hypothesis that UMLs and AMIs will each be maintained in an active state, as manifested by above-baseline high-gamma power, but that the amplitude of this high-gamma power will be markedly higher for AMIs. Furthermore, this differential level of high-gamma power will be explained by the fact that the (pattern of) electrodes representing the AMI will exhibit higher interregional PAC than will the UMI. Because Voytek and colleagues [69] have shown that PAC in posterior regions tends to be anchored in the alpha band (as contrasted with a bias toward theta-paced PAC in frontal cortex), we expect that the attention-related changes in interregional PAC in ITS, mid fusiform gyrus, VO1, and/or STS, may also be concentrated in the alpha band. Assuming that we do find evidence for a phase-encoded selection mechanism in our working memory task, an important question will be to determine the source of the low-frequency oscillation clocking the predicted selection-related increase in interregional PAC. Our *a priori* working hypothesis is that this will be the “posterior alpha” that is prominent in EEG electrodes

over parietal cortex, strongly associated with visual attention (e.g., [50, 59, 67]), and widely assumed to be generated by thalamocortical circuits encompassing the caudal intraparietal sulcus.

One important point highlighted in our research plan is the fact that study [70], on which the data analysis plan of the present protocol was based, is “limited” to four patients, and to 20-30 trials/condition/patient, it nonetheless featured sufficient power to support, for example, trial-by-trial prediction of behavioral RT, and msec-level resolution of the onset of event-related phase-encoding (i.e., of phase-encoded selection).

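### Sub-study B: if electrodes are chosen on delay-period data, the text does not keep those trials out of the Stage 2 high-gamma tests, which can then be circular

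*Combined protocol and SAP*

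**What the plan says.** Statistical Considerations sets out two stages for Sub-study B. Stage 1 first trains classifiers on high-gamma values from the sample epochs and applies them to the delays. The plan notes that this presumes one neural code for perceiving and remembering. It therefore also prepares a fallback that holds out one trial at a time, in which "MVPA classifiers will be iteratively trained and tested on data from the Delaypost-cue epochs". Which data will train the classifiers is left open until the team has begun work on them.

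If all three stimuli can be decoded, the top tenth of electrodes for each stimulus go forward, described as "the electrodes with the highest loadings in the importance map of the trained classifier corresponding to each stimulus". If MVPA is unstable, the back-up is to measure each electrode's "selectivity for each item in the stimulus set with receiver operating characteristic (ROC)-based analyses". Neither the epoch nor the trials for that back-up are named.

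The plan says that "Stage 1 of the analyses will necessarily have an exploratory quality", and then that "Stage 2 will effect the test of the phase-encoded selection hypothesis". Stage 2 predicts that attended (AMI) and unattended (UMI) memory items are both active, "as manifested by above-baseline high-gamma power", and that "the amplitude of this high-gamma power will be markedly higher for AMIs". Baseline is not defined.

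Sub-study A keeps the two steps apart: "Data analysis from the Attention Task will focus on electrodes identified in the Receptive Field Mapping task".

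**The concern.** An electrode can rank high for a category partly because of chance fluctuation in the trials used to rank it. If the same trials then supply the Stage 2 test, that chance part is counted as effect. Holding one trial out protects the decoding accuracy only: over the folds every trial helps to train the classifiers whose loadings choose the electrodes.

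The Specific Aims ask whether UMIs are carried by elevated activity at all. Depending on how the classifiers are labelled, reuse can create a difference between AMI and UMI or create a UMI effect. The plan claims adequate power within single subjects and needs interpretable data from only 4 patients. Agreement across patients would give no protection, because the artefact would recur in each of them.

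**Working it through.** The plan gives no significance level, effect size or error rate for Stage 2, so there is no figure of its own to reproduce. The check is a null calculation and simulation.

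**Inputs from the document.** 128 research channels (Data collection and processing). Top 10%, so 0.10 × 128 = 12.8, about 13 electrodes per category. Three categories, with one AMI, one UMI and one irrelevant on each trial. At least 96 trials (Sub-study B, experimental procedure) or 40 (Statistical Considerations); both were run.

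**Assumptions.** Gaussian noise with no true effect; correlation 0.3 between electrodes through noise shared within a trial; electrodes ranked by signed mean difference; paired t test over trials at two-sided 5%, counting only the predicted direction (nominal 2.5%); 600 data sets per setting.

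**Formula.** For each electrode, w = mean(labelled trials) − mean(other trials). With cued-item labels one third of trials are labelled, so SE(w) = √(0.7) × √(1/n₁ + 1/n₂). The mean of the top tenth of a standard normal is 0.1755/0.10 = 1.755.
- 96 trials: 0.837 × √(1/32 + 1/64) = 0.181; × 1.755 = 0.318 SD expected by chance (simulated 0.314).
- 40 trials: 0.837 × √(1/13.3 + 1/26.7) = 0.281; × 1.755 = 0.49 SD (simulated 0.485).

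The shared noise cancels in the AMI − UMI difference, whose SD per trial is about √(2 × 0.7/13) = 0.328. Then t ≈ 0.314/(0.328/√96) = 9.4, and 0.485/(0.328/√40) = 9.3. Rejection is almost certain at either sample size.

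| Selection and test | Trials | AMI > UMI | UMI > irrelevant |
|---|---|---|---|
| Reused, cued labels | 40 / 96 | 100% / 100% | 2.0% / 2.0% |
| Reused, category-present labels | 40 / 96 | 2.3% / 2.8% | 100% / 100% |
| Split halves, cued labels | 40 / 96 | 3.8% / 2.5% | 2.0% / 2.2% |
| Split halves, category-present labels | 40 / 96 | 3.8% / 2.7% | 2.0% / 2.2% |

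**Why the label matters.** With category-present labels, AMI and UMI both lie in the labelled group, so their difference is unbiased while each exceeds the irrelevant category. Each also lies w/3 above the electrode's overall mean: 0.318/3 = 0.106 SD at 96 trials. Against a separate, equally noisy baseline on each trial the SE is √(2 × (0.3 + 0.7/13))/√96 = 0.086, so t ≈ 1.2 and about 23% reject. Simulation gave 17-23%. With cued labels the UMI lies w/3 below the overall mean. It is then lowered against a separate baseline but not against the irrelevant category.

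**Other settings.** Ridge classifiers and ROC ranking, with signed selection and cued labels, also gave 100% false AMI > UMI. With absolute loadings that figure was 9.2% in the set-up above, with no mean bias (−0.002 SD), and 4-11% over all runs.

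**Decoding gate.** The plan sends MVPA electrodes forward only if decoding succeeds. Modelled as leave-one-out accuracy above 1/3 at p < 0.05 (96 trials, 300 data sets per setting), about 5-7% of pure-noise data sets passed. With a real category signal of 0.5 or 1.0 SD and AMI equal to UMI, 46-79% passed. Among those, reused trials with cued labels gave false AMI > UMI in 99-100%, and split halves in 1-4%.

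**Sample-epoch selection.** With independent sample and delay noise, all tests stayed at 2-3%. With noise shared within a trial (correlation 0.2) and labels by item shown, UMI > irrelevant was false in 45%, while AMI > UMI stayed at 2-3%. Labelling sample epochs by the later-cued item instead gave false AMI > UMI in 45-47%. Over other runs at correlations of 0.2-0.3, false UMI > irrelevant ranged from 21% to 94%. Against a separate pre-trial baseline the UMI test stayed at 2-6%.

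**The case against.** The strongest reply is that the circular route is only one branch. Sample-epoch training comes first and delay training is a fallback. The sentence on loadings refers to a single trained classifier, which may mean the sample-trained one. The error also needs reused trials, a feature close to high-gamma power and signed loadings, and its direction depends on the label. This stands, and it is why the point is conditional. But the plan permits the fallback, gives a reason why it may be needed, and leaves the ROC epoch open.

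A second reply is the decoding gate. It does stop most pure-noise data sets. It does not help in the case that matters most for AMI > UMI: real category information, equally strong for both items.

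A third is the plan's own description of Stage 1 as exploratory. That does not extend to Stage 2, which is presented as the hypothesis test.

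A reader might infer that no safeguard exists anywhere. The documents do not support that. The quality-assurance text also points to the grant application, which was not available, and some pages of the protocol were removed.

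**Conclusion.** The point holds in conditional form. The text permits electrode choice on delay data and does not require separate trials for the Stage 2 high-gamma tests. With reused trials, a high-gamma-like feature and signed loadings, cued labels make a false AMI > UMI nearly certain (about 100%, against about 2-4% with split halves). Category-present labels leave AMI > UMI near nominal but produce a false UMI effect: about 20% against a separate noisy baseline and 100% against the irrelevant category, at electrode correlation 0.3. With absolute loadings the inflation of AMI > UMI is small, about 4-11%.

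Three stronger readings are not supported. The rates are not the study's error rate, because labels, loading sign, feature and baseline are unstated and the noise model is assumed. In these runs no single labelling produced both a false AMI > UMI and a false UMI effect. Bias in the PAC tests has not been shown, because PAC was not simulated. Sample-trained selection is not circular in the same direct way, though it can leak if noise persists within a trial and the irrelevant category serves as baseline.

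**What to change.** Add to Stages 1 and 2 of Sub-study B:

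> If electrodes, feature or window are chosen on delay-period data (MVPA or ROC), Stage 2 tests will use only trials not used for that choice (both delays of a trial kept together), or a permutation test that repeats the selection step in every permutation. If electrodes are chosen on sample epochs of the same trials, the above-baseline test will use a named pre-sample baseline from the same trial; a comparison with the irrelevant category will use independent trials. Classifier labels, loading rule (signed or absolute) and baseline will be fixed before Stage 2.

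For sample epochs, the label should be the item shown, since the cue comes later.

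Patient procedures do not change. The cost is power if trials are split. Assuming true effects of 0.7 SD (AMI) and 0.3 SD (UMI), signed loadings and cued labels, split-half power at electrode correlation 0 / 0.3 was:
- UMI above a per-trial baseline: 31% / 9% with 40 trials, 81% / 30% with 96.
- AMI > UMI: 35% / 54% with 40 trials, 93% / 99.6% with 96.

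Sample-epoch selection or the permutation test keeps all trials; the permutation test was not simulated. The minimum of 96 trials in the procedure and 40 in the statistical section should be reconciled, because a split leaves 48 or 20 for testing.
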